8.3.1. PEGPH20

8.3.1.1. PEGPH20 Administration

The PEGPH20 dose will be individually calculated for all dosing visits according to the subject's screening weight. In calculating the dose, there will be no downward adjustment to "ideal" body weight. Doses should be re-adjusted if the subject's weight changes by >10%. If the subject's weight changes by $\le 10\%$, no adjustment is necessary unless the site has a standard procedure to adjust doses based upon current weight. The dispensing pharmacist will verify the dose accuracy with a qualified study staff member. The appropriate dose will be diluted as per the instructions provided in a separate pharmacy manual.

After completion of pre-dose activities, PEGPH20 will be administered as an IV infusion over 10 minutes, approximately 1 mL/minute (a window of +2 minutes is allowed, i.e., infusion can be 10 to 12 minutes), under observation by qualified clinic staff. The volume and/or duration of PEGPH20 administration may change at the discretion of the Sponsor, based upon safety information. The study nurse or alternate designee by the Investigator will record the time the infusion was started and stopped. A saline flush should follow IV delivery of the complete PEGPH20 dose as per standard of care for flushing IV lines. Only a peripheral line should be used for the administration of PEGPH20 (heparin flushes should not be used on the same line as PEGPH20), but heparin flushes may be used for central lines as per standard of care. In the event that peripheral venous access cannot be obtained, the central line may be used. If this happens, ensure the line is flushed with saline (minimum of 10 mL) prior to administering PEGPH20 and after administering PEGPH20. Ensure the PEGPH20 administration is not done immediately before or after the central line has been flushed with a heparin flush (i.e., ensure the line is flushed with a heparin flush no earlier than 1 hour before or after the PEGPH20 administration).

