8.3.2. Pembrolizumab

8.3.2.1. Pembrolizumab Administration

Pembrolizumab will be administered by IV infusion at a dose of 2 mg/kg (in Dose Escalation) or 200 mg (in Dose Expansion) over 30 minutes once every 21 days on Day 1 of each cycle, 4-6 hours after the PEGPH20 dose.

The pembrolizumab dose will be individually calculated for all infusion visits in Dose Escalation according to the subject's screening weight. In calculating the dose, there will be no downward

adjustment to "ideal" body weight unless institution policy requires it. Doses should be readjusted if the subject's weight changes by >10%. If the subject's weight changes by $\le 10\%$, no adjustment is necessary unless the site has a standard procedure to adjust doses based upon current weight.

All Cycle Day 1 administrations of pembrolizumab should occur 4-6 hours after PEGPH20 administration.

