- Frequency and percentage of dose interruption by reason, including adverse event and other
- Frequency and percentage of interrupted doses restarted
- Actual dose intensity (ADI) per cycle is defined as the cumulative dose divided by number of adjusted treatment cycles.
  - The weight-adjusted cumulative dose administered for PEGPH20 (in both Dose Escalation and Dose Expansion portions) and pembrolizumab (in the Dose Escalation portion only) is the sum of the respective doses administered at a given visit, divided by the subject's weight measurement (kg) at Screening. Cumulative dose for pembrolizumab (in the Dose Expansion portion only) is defined as the sum of administered doses.
  - If the last dosed cycle is Cycle 1, then number of adjusted treatment cycles is considered to be 1. If the last dosed cycle is Cycle 2 or beyond, then the number of adjusted treatment cycles will be calculated as [(End date of last cycle First dose date + 1) / 21], where the end date of last cycle is calculated as [First dose date of last cycle + (Number of doses received or omitted in the last cycle up to the last dose received) \* 20 / 3] for PEGPH20 and (Dose date + 20) for pembrolizumab. For PEGPH20, if the day of the visit of first dose date of last cycle is not 1, then an adjustment should be made by subtracting 7 or 14 depending on whether the day is 8 or 15 respectively.
- The planned dose intensity (PDI) for PEGPH20 is calculated as follows:
  - For the Dose Escalation portion, if the number of adjusted treatment cycles is 1, then the planned dose intensity per cycle (ug/kg) for each individual dosing cohort will be calculated as [(Dose level in ug/kg) \* Number of doses received or omitted up to the last dose received in Cycle 1]. Else, the planned dose intensity per cycle (ug/kg) for each individual dosing cohort will be calculated as [(Dose level in ug/kg) \* 3].
  - For the Dose Expansion portion, if the number of adjusted treatment cycles is 1, the planned dose intensity per cycle (ug/kg) will be calculated as [(RP2D dose in ug/kg) \* Number of doses received or omitted up to the last dose received in Cycle 1]. Else, the planned dose intensity per cycle (ug/kg) will be calculated as [(RP2D dose in ug/kg) \* 3].
- The PDI for pembrolizumab is calculated as follows:
  - For the Dose Escalation portion, the planned dose intensity per cycle is 2 mg/kg.
  - For the Dose Expansion portion, the planned dose intensity per cycle is 200 mg.

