- The Relative dose intensity (RDI) (percent) is defined as follows:
  - [(ADI per cycle) / (PDI per cycle)] \* 100%

In addition to descriptive summary of relative dose intensity, the frequency and percentage of subjects will be presented for the following relative dose intensity

categories:  $\geq$ 90%, 80% to <90%, 70% to <80%, 60% to <70%, 50% to <60%, and <50%.

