#### 4.9.5 Vital Signs and Body Weight

Vital signs assessments will be performed pre dose on Day 1, Day 8, and Day 15 of all cycles and at the End of Treatment visit. On all other days, vital signs will be evaluated for clinically significant AEs.

Vital signs including blood pressure (systolic and diastolic), heart rate (beats/min), respiratory rate (breaths/min), body temperature (°C) and weight (kg) will be summarized by visit and by cancer type and in total using descriptive statistics.

Height (cm), weight (kg) and body surface area (BSA; m^2) will be summarized by visit using descriptive statistics. BSA is calculated using DuBois formula as:

$$BSA = 0.007184 * W^{0.425} * H^{0.725}$$

By-subject listings of vital signs and body weight will also be provided.

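### SAP 4.9.2 scales every per-kg dose to Screening weight, so doses recalculated on a new actual weight give a relative dose intensity other than 100% even when dosing is fully compliant

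*SAP*

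**What the plan says.** SAP Section 4.9.2 builds RDI in three steps.

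- The weight-adjusted cumulative dose is the "sum of the respective doses administered at a given visit, divided by the subject's weight measurement (kg) at Screening". This applies to PEGPH20 in both portions and to pembrolizumab in Dose Escalation. Pembrolizumab in Dose Expansion is a flat dose and is summed without any weight.
- Actual dose intensity (ADI) is the cumulative dose divided by the number of adjusted cycles.
- RDI is ADI over planned dose intensity (PDI). Beyond a single cycle, the PEGPH20 plan is the cohort dose level or the RP2D times 3 per cycle. For pembrolizumab, "For the Dose Escalation portion, the planned dose intensity per cycle is 2 mg/kg". Neither plan is tied to a particular body weight.

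The SAP then bands the result: "the frequency and percentage of subjects will be presented for the following relative dose intensity" categories, from at least 90% down to below 50% in ten-point steps.

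The protocol's default dosing weight is the Screening weight, but it does not stop there. For PEGPH20, "Doses should be re-adjusted if the subject's weight changes by >10" per cent (Section 8.3.1.1). For pembrolizumab, "Doses should be readjusted if the subject's weight changes by >10" per cent (Section 8.3.2.1). For smaller changes, Section 8.3.1.1 says that "no adjustment is necessary unless the site has a standard procedure to adjust doses based upon current weight", and Section 8.3.2.1 has the same exception.

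The SAP makes no provision for a dose recalculated on a later weight, and its Section 5, which lists changes from the protocol's analysis, does not mention the matter.

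**The concern.** When a dose has been recalculated on a new weight, numerator and denominator use different weights. The amount given reflects the new weight, the divisor is the old one, and the comparator is a nominal per-kg figure. A subject who loses weight and is re-dosed as the protocol directs then appears under-dosed. A subject who gains weight appears over-dosed.

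At stake is how a descriptive exposure table reads. RDI is one of the exposure outputs named in protocol Section 11.1.7, and tolerability is an objective of both portions. The cohorts are small: SAP Section 4.7.2 reports 17 NSCLC and 25 gastric subjects enrolled in Dose Expansion. If all were dosed, one subject placed in the wrong band moves that band by 1/17 = 5.9 or 1/25 = 4.0 percentage points.

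**Working it through.** The documents state no RDI value, so there is no planned figure to reproduce. The check applies the SAP's own formulas to simple dosing histories.

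**Reading of ADI.** The ADI line says only cumulative dose, but the weight-adjusted definition is nested beneath it and PDI is per kg. The per-kg reading is the only one with matching units.

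**Inputs from the documents.** PEGPH20 is given 3 times per 21-day cycle. PDI is level × 3 for PEGPH20 and 2 mg/kg for pembrolizumab in Dose Escalation. The divisor is Screening weight.

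**Assumed inputs.** 6 cycles, and weight changes of given size and timing, because the documents hold no weight-change data. For scale only, the pembrolizumab-alone NSCLC median PFS of 3.7 months cited in protocol Section 4.6.1 is 3.7 × 30.4375 / 21 = 5.4 cycles.

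**Adjusted cycles, on-time dosing.** The last cycle starts on day 1 + 21 × 5 = 106 and its end date is 106 + 3 × 20/3 = day 126. Adjusted cycles = (126 − 1 + 1)/21 = 6. With every dose on Screening weight, RDI = 100%, so the rule is coherent for the default case.

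**General result.** For full, on-time dosing, RDI = 100% × mean(dosing weight / Screening weight). If a share f of doses is given on a weight changed by the fraction c, RDI = 100% × (1 + f × c). Intensity per kg of the weight dosed on is 100% throughout.

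**Six cycles, 18 PEGPH20 doses:**

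| Recalculated from | f | 15% loss | 20% loss | Loss needed to fall below 90% (0.10/f) |
|---|---|---|---|---|
| Cycle 2 | 15/18 | 87.5% | 83.3% | more than 12% |
| Cycle 3 | 12/18 | 90.0% | 86.7% | more than 15% |
| Cycle 4 | 9/18 | 92.5% | 90.0% | more than 20% |

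Pembrolizumab at 2 mg/kg, one dose per cycle, has the same f and gives the same percentages.

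**Other treatment lengths, recalculated from Cycle 2.** Over 4 cycles, losses of 15% and 20% read 88.75% and 85.0%. Over 8 cycles they read 86.9% and 82.5%, and a 15% gain reads 113.1%. Over 3 cycles f = 6/9, so only a loss above 15% leaves the top band.

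**Site-procedure dosing.** A 10% loss from Cycle 2 of 6 reads 1 − (15/18) × 0.10 = 91.7%, still in the top band. If one dose in the recalculated cycles (not the last) is also omitted, it reads (3 + 14 × 0.90)/18 = 86.7%, against 17/18 = 94.4% when scaled to the dosing weight.

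**Check of the remedy.** Dividing each dose by the weight used to calculate it returns 100.0% in every full-dose, on-time history. A real reduction from 3.0 to 2.6 µg/kg in all cycles still shows, as 2.6/3.0 = 86.7%.

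**The case against.** The best defence is that Screening weight is a baseline convention. It is the protocol's default dosing weight, and the SAP indexes to entry elsewhere: subjects are analysed by initial cohort, and PDI uses the cohort dose level although intra-subject escalation is allowed. That would hold if the plan were also fixed on Screening weight. It is not: PDI is nominal per kg, and the SAP does not state such a convention.

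Other parts of the defence stand.

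- A 15% to 20% loss by Cycle 2 or 3 is a large early change in subjects enrolled with ECOG 0 or 1, and nothing in the documents shows how often it occurs.
- Omissions, reductions, delays and interruptions have their own tables in SAP 4.9.2, and SAP 4.9.5 summarises weight by visit and adds: "By-subject listings of vital signs and body weight will also be provided". A reader can investigate an odd RDI, although those outputs do not correct the band.
- Scaling to the dosing weight will not reveal a recalculation that was due but not made. The Screening-weight rule does not reveal it either.

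Two stronger readings are tempting and are not supported.

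- A reader might infer that ideal-weight dosing of pembrolizumab, which the protocol excludes for "body weight unless institution policy requires it", is also misreported. Take an assumed 80 kg subject dosed on 68 kg: the subject receives 2 × 68/80 = 1.7 mg per actual kg, and 85.0% describes that correctly against a 2 mg/kg plan. Which target is wanted there is a matter of choice.
- A reader might infer that weight gain hides omitted doses. A 15% gain from Cycle 4 of 6, with 2 of 18 doses omitted in the recalculated cycles (neither the last), reads (9 + 7 × 1.15)/18 = 94.7% instead of 16/18 = 88.9%. The RDI value and band shift, but the omissions still appear in their own table.

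**Conclusion.** The point holds for per-kg doses recalculated on a new actual weight. For those doses, weight-adjusted cumulative dose, ADI and RDI are off by the ratio of dosing weight to Screening weight: too low after loss, too high after gain. Early losses of 15% to 20% can move a fully dosed subject from the top band to 80% to below 90%. Changes of about 10% or less, or later ones, usually do not, unless doses are also omitted.

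The consequence is minor. RDI is descriptive and feeds no decision rule. The ORR tests, the DLT analysis, the sample size, flat-dose pembrolizumab and doses calculated on Screening weight are untouched. The percentages rest on assumed weight changes, timing and number of cycles. The effect on the actual tables could be nil. It is a worthwhile correction to the derivation, not a threat to any conclusion of the trial.

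**What to change.** In SAP 4.9.2, divide each administered per-kg dose by the actual body weight used to calculate it, which is Screening weight unless the dose was recalculated, and sum the per-kg values. This also handles repeated recalculation and weight recovery.

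- Where the dosing weight was not recorded, keep Screening weight, flag the subject and footnote the number flagged.
- Do not assume that a change above 10% led to recalculation. A subject with a 15% loss still dosed on Screening weight would then read 1/0.85 = 117.6% for those doses.
- Report any pembrolizumab subjects dosed on ideal weight in a footnote and do not rescale them.

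The cost is a wording change and minor programming. The documents do not say whether the weight used for each dose is captured, so some subjects may have to stay on Screening weight. No dosing rule changes.

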#### 3.1.2 Phase 1b Dose Expansion Portion

Approximately 51 HA-high subjects will be studied in the Dose Expansion portion at the RP2D identified in the Dose Escalation portion:

- Approximately 30 subjects with Stage IIIB or IV NSCLC, previously untreated or treated and having failed no more than 1 previous platinum-based chemotherapy (refer to Inclusion Criterion #3)
- Approximately 21 subjects with relapsed/refractory gastric adenocarcinoma having failed no more than 2 previous chemotherapy regimens.

In Dose Expansion, PEGPH20 will be administered on Day 1, Day 8, and Day 15 of each 21-day cycle (i.e., 3 doses / cycle) and pembrolizumab (200 mg every 21 days) on Day 1 of each cycle (i.e., 1 dose / cycle), 4-6 hours after the completion of PEGPH20 administration. The dosing schedule is shown in Table 2.

If a dose of PEGPH20 is missed on Day 1 of Cycle 2 or beyond, the cycle will continue as scheduled. If it is known that pembrolizumab will be missed or held on Day 1, PEGPH20 should also be held and the cycle will not start until the first dose of pembrolizumab is administered. This will require planning such that the dose of PEGPH20 can be given before the pembrolizumab dose is set to resume.

Time point	PEGPEM Treatment by Treatment Group		
Subjects with NSCLC			
Cycle 1 and B	eyond (Each Cycle 21 Days)		
Week 1			
Day 1	PEGPH20		
	Pembrolizumab (4-6 hours after PEGPH20)		
Week 2			
Day 8	PEGPH20		
Week 3			
Day 15	PEGPH20		
Subjects with Gastric Adenocarcinoma			
Cycle 1 and B	eyond (Each Cycle 21 Days)		
Week 1			
Day 1	PEGPH20		
	Pembrolizumab (4-6 hours after PEGPH20)		
Week 2			
Day 8	PEGPH20		
Week 3			
Day 15	PEGPH20		

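### The SAP's end-date rule for the last PEGPH20 cycle makes relative dose intensity slightly too low when the last dose falls on Day 1 or Day 8 of Cycle 2 or later

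*SAP*

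**What the plan says.** SAP 3.1.2 gives the schedule: "PEGPH20 will be administered on Day 1, Day 8, and Day 15 of each 21-day" cycle, so three doses at 7-day intervals. SAP 4.9.2 defines RDI as actual dose intensity per cycle divided by planned dose intensity per cycle. Actual intensity is the cumulative dose divided by a number of adjusted treatment cycles, which is obtained in one of two ways.

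- **Last dosed cycle is Cycle 1.** "If the last dosed cycle is Cycle 1, then number of adjusted treatment cycles is considered to be 1". Planned intensity is then the dose level times "Number of doses received or omitted up to the last dose received in Cycle 1", so it is pro-rated.
- **Last dosed cycle is Cycle 2 or later.** Adjusted cycles are ("End date of last cycle First dose date + 1) / 21"), read as end date minus first dose date; the minus sign is lost in the extracted text. For PEGPH20 the end date is the first dose date of the last cycle plus k × 20/3, where k is the "Number of doses received or omitted in the last cycle up to the last dose received". If the first dose of that cycle was on Day 8 or Day 15, "an adjustment should be made by subtracting 7 or 14 depending on whether the day is 8 or 15 respectively". Planned intensity is the dose level times 3.

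RDI is summarised descriptively and in fixed bands that include their lower limit, among them "80% to <90%, 70% to <80%, 60% to <70"%.

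**The concern.** The term k × 20/3 divides a 20-day offset into three equal parts, and one day is then added to the whole span. That extra day completes a 21-day cycle when k = 3, because 20 + 1 = 21. It does not scale down when k is 1 or 2. The last partial cycle is therefore counted as slightly longer than the 7 or 14 days that its doses represent, while planned intensity stays at three doses per 21 days.

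The SAP's neighbouring rules suggest that this was not intended. For pembrolizumab the end date is the dose date plus 20, which with the added day gives exactly 21. For Cycle 1 the planned intensity is pro-rated exactly. As a result, two fully compliant subjects are treated differently: one who stops at Cycle 1 Day 1 gets 100%, and one who stops at Cycle 2 Day 1 gets less.

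At stake are the RDI mean and the band counts in a small table. SAP 4.7.2 reports 17 NSCLC and 25 gastric subjects enrolled in Dose Expansion. If all are tabulated, one subject is 1/17 = 5.9% or 1/25 = 4.0% of a column.

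**Working it through.** **Inputs.** Three doses per 21-day cycle, 7 days apart (SAP 3.1.2). Adjusted cycles, end date, planned intensity and band limits of 90, 80, 70, 60 and 50% (SAP 4.9.2). The plan gives no worked RDI value to reproduce.

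**Assumptions.** Dosing is on schedule, every administered dose is a full dose, and the fractional end date is carried into the division.

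**Formulas.** Let C ≥ 2 be the last dosed cycle, k the dose count in it, and x the number of doses received.

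- SAP adjusted cycles = [21(C − 1) + 20k/3 + 1] / 21
- Reference adjusted cycles = (C − 1) + k/3
- RDI = x / (3 × adjusted cycles)

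**Length given to the last cycle**

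| k (last dose) | SAP days | Days represented | SAP fraction | Correct fraction |
|---|---|---|---|---|
| 1 (Day 1) | 20/3 + 1 = 7.67 | 7 | 0.3651 | 0.3333 |
| 2 (Day 8) | 40/3 + 1 = 14.33 | 14 | 0.6825 | 0.6667 |
| 3 (Day 15) | 20 + 1 = 21 | 21 | 1.0000 | 1.0000 |

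**Fully dosed subjects (correct RDI 100%)**

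| Last dose | Doses | 3 × SAP adjusted cycles | SAP RDI |
|---|---|---|---|
| Cycle 2 Day 1 | 4 | 4.095 | 97.67% |
| Cycle 2 Day 8 | 5 | 5.048 | 99.06% |
| Cycle 3 Day 1 | 7 | 7.095 | 98.66% |
| Cycle 4 Day 1 | 10 | 10.095 | 99.06% |
| Cycle 12 Day 1 | 34 | 34.095 | 99.72% |
| Any Day 15 | 3C | 3C | 100% |

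The largest relative shortfall is 1 − 4/4.095 = 2.3%, at Cycle 2 Day 1. When the last dosed cycle is Cycle 1, adjusted cycles are 1 and planned intensity is k doses, so RDI = x/k and there is no bias.

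**Subjects exactly on a band limit**

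| Last dose | Received / expected | Correct | SAP |
|---|---|---|---|
| Cycle 2 Day 1 | 2/4 | 50% | 48.84% |
| Cycle 2 Day 8 | 4/5 | 80% | 79.25% |
| Cycle 2 Day 8 | 3/5 | 60% | 59.43% |
| Cycle 4 Day 1 | 9/10 | 90% | 89.15% |
| Cycle 4 Day 1 | 8/10 | 80% | 79.25% |
| Cycle 4 Day 1 | 7/10 | 70% | 69.34% |
| Cycle 4 Day 1 | 6/10 | 60% | 59.43% |
| Cycle 4 Day 1 | 5/10 | 50% | 49.53% |

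Each drops one band, so all five limits are affected. Every combination of last cycle (1 to 17), k and number of full doses was checked, and every band change was at an exact limit. Dose reductions can also place a subject just above a limit. In the worst case, Cycle 2 Day 1, a correct RDI from 90% up to 90% × 4.095/4 = 92.1% would be reported below 90%.

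**If the end date is made a whole day.** Truncation gives +6, +13 and +20, hence 7, 14 and 21 days and no bias. Rounding to the nearest day gives +7, +13 and +20. Then k = 1 is still biased: 4 × 7 / (21 + 7 + 1) = 28/29 = 96.55% at Cycle 2 Day 1.

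**The case against.** The strongest reply is that an end date is naturally a whole day, and that truncation makes the rule exact. The arithmetic is right, but the SAP does not say to truncate. Where it wants an integer it says so, as in the age formula in SAP 4.6.1. Read as written, the fraction stays, and ordinary rounding leaves the Day 1 case wrong. SAP 4.1 requires outputs to be independently checked, and two programmers could reasonably obtain different RDIs from this text. The defence therefore shows that a rule is missing; it does not show that the formula is sound.

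The second reply is that the band changes are knife-edge cases, and this largely stands. Take 4 of 5 doses ending at Cycle 2 Day 8. If Cycle 2 starts one day early, RDI is 28/34 = 82.4% correctly and 28/34.33 = 81.6% by the SAP, the same band. One day late, it is 28/36 = 77.8% and 28/36.33 = 77.1%, again the same band. The visit window is ±2 days. Protocol 8.3.1.1 also allows doses to follow current weight, while SAP 4.9.2 divides by Screening weight, so exact ratios will be uncommon. The bias is also smaller than permitted schedule variation: under a correct formula, a fully dosed subject ending at Cycle 2 Day 1 falls to 28/29 = 96.6% if that cycle starts one day late and 28/30 = 93.3% if two days late.

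Two stronger readings are tempting. A reader might infer that anyone whose last dose is on Day 1 or Day 8 is understated, or that only Day 15 finishers can reach 100%. The separate Cycle 1 rule contradicts both. A reader might also infer that everyone who missed 1 of 5 or 1 of 10 doses is put in too low a band. That holds only for on-schedule full dosing with the last dose on Day 1 or Day 8 in Cycle 2 or later.

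**Conclusion.** The formula is wrong as written, within a narrow scope: last dosed cycle is Cycle 2 or later, and last PEGPH20 dose on Day 1 or Day 8. There the denominator is 2/3 or 1/3 day too long. The conclusion rests on keeping the fractional end date, and the quoted sizes also assume on-schedule dosing. A fully dosed, on-schedule subject stays in the top band under either formula. It would be a mistake to infer any effect on efficacy, on safety conclusions or on the dose decision: RDI is a descriptive exposure measure and no hypothesis test or endpoint uses it. This is a minor correction.

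**What to change.** In SAP 4.9.2, replace the PEGPH20 end date of the last cycle by:

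`First dose date of last cycle + 7 × k − 1`

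with k as the SAP already defines it ("Number of doses received or omitted in the last cycle up to the last dose received"). Keep the existing subtraction of 7 or 14 days when the first dose of that cycle is on Day 8 or Day 15. The last cycle then counts as 7, 14 or 21 days for k = 1, 2 or 3. A subject with every dose on schedule has RDI 100% whichever day is last, and exact limit values stay in their own band. At the least, state that the end date is truncated to a whole day, which gives the same result.

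The cost is one formula in the SAP and one line in the exposure program. No data collection, sample size or other analysis changes.

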6.1.1. Phase 1b Dose Escalation

This portion of the study is a single-arm, dose escalation study of PEGPH20 in combination with pembrolizumab subjects with relapsed/refractory NSCLC after failing at least 1 previous platinum-based therapy (refer to Inclusion Criterion #2) and subjects with relapsed/refractory gastric adenocarcinoma after failing at least 1 previous chemotherapy regimen. Using a standard 3+3 dose escalation design, approximately 3 to 6 subjects in each cohort will receive PEGPH20 + pembrolizumab. PEGPH20 will be administered on Day 1, Day 8 and Day 15 of each 21-day cycle to consecutive cohorts in increasing dose levels (1.6, 2.2, 2.6, 3.0, and 4.0 μ g/kg). Pembrolizumab will be administered on Day 1 of each cycle, 4-6 hours after the dose of PEGPH20. If the MTD is not reached at 4.0 μ g/kg, higher doses may be evaluated. If \geq 2 subjects experience a DLT at the 1.6 μ g/kg dose level, Cohort -1 will be opened and subjects will be dosed at 1.0 μ g/kg on Day 1, Day 8 and Day 15 of each 21-day cycle. The RP2D of PEGPH20 will be the MTD determined in Dose Escalation or the Sponsor may decide to choose a dose lower than the MTD and which has completed evaluation in Dose Escalation and is found to be safe and tolerable to evaluate in Dose Expansion.

The number of cohorts studied and number of subjects exposed to a given dose level will depend on the doses tested. It is anticipated that up to 5 dose levels will be studied for a total of approximately 30 subjects exposed to study medication. The dose allocation for 5 cohorts of subjects assigned to the 5 preselected dose levels and 1 cohort assigned to the preselected dose of $1.0 \,\mu\text{g/kg}$ (if ≥ 2 subjects experience a DLT at $1.6 \,\mu\text{g/kg}$ dose level) is shown as an example in Table 4. The study medication dosing and treatment schedule are shown in Table 5.

Safety data from all subjects dosed will be reviewed to determine the RP2D. Dose escalation will be guided by safety data from each subject during the 21 days following their first dose of PEGPH20. Intra-subject dose escalation to the next PEGPH20 dose studied may be allowed if the Investigator deems it in the best interest of the subject and after discussion with the Sponsor and provided the next PEGPH20 dose studied has been determined not to have exceeded the MTD.

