PEGPH20. Intra-subject dose escalation to the next PEGPH20 dose studied may be allowed if the Investigator deems it in the best interest of the subject and after discussion with the Sponsor and provided the next PEGPH20 dose studied has been determined not to have exceeded the MTD.

- If none of initial 3 subjects in a given cohort experience a DLT within 21 days of starting treatment, enrollment and dosing may proceed at the next planned dose level.
- If 1 of 3 initial subjects at a given dose level experiences a DLT within the first 21 days of treatment, 3 additional subjects will be enrolled and dosed at the same dose level. If ≤1 of 6 subjects experiences a DLT, dose escalation may continue to the next planned higher dose.
- If ≥2 subjects at a given dose level experience a DLT within the first 21 days of treatment, that dose level will be considered to have exceeded the MTD and dose escalation will be stopped. If the previous dose level did not already have 6 subjects treated with ≤1 DLT, enrollment and dosing will then resume in the previous dose level with additional subjects up to a total of 6 subjects. The highest dose level at which no more than 1 of 6 evaluable subjects has experienced a DLT in the first 3 weeks of treatment will be considered the MTD for the PEGPEM combination. The RP2D will be based on the overall safety profile.
- If  $\geq 2$  subjects at the 1.6 µg/kg dose level experience a DLT within the first 21 days of treatment, Cohort -1 will be opened at a lower dose level of 1.0 µg/kg.

**Note**: Additional subjects may be enrolled in each cohort to further assess the tolerability of PEGPEM and determine an acceptable safety profile prior to the enrollment in the next dose level and Dose Expansion portion of the study.

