#### 4.4.2 Safety Population

The Safety Population analysis set is defined as all enrolled subjects in either Dose Escalation or Dose Expansion portion of the study, who receive at least 1 dose of any study medication (PEGPH20 or pembrolizumab). The Safety Population will be used for drug exposure, demographics and safety analyses, including AE, labs, and deaths. Subjects will be analyzed according to the initial cohort actually assigned.

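### PEGPH20 planned dose intensity is fixed at the cohort's dose level although subjects may escalate, so relative dose intensity is inflated for any subject who does

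*SAP*

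**What the plan says.** SAP 4.9.2 builds RDI in three steps.

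- Numerator: "Actual dose intensity (ADI) per cycle is defined as the cumulative dose divided by number of adjusted treatment cycles". For PEGPH20 the cumulative dose is the sum of the doses given, divided by screening weight.
- Denominator for the Dose Escalation portion, once there is more than one adjusted cycle: "the planned dose intensity per cycle (ug/kg) for each individual dosing cohort will be calculated as [(Dose level in ug/kg) \* 3". In the one-cycle case the multiplier is the number of doses received or omitted in Cycle 1.
- Ratio: "ADI per cycle) / (PDI per cycle", as a percentage. It is summarised descriptively and in six classes. The top class is ≥90% with no upper limit, and the lowest is <50%.

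The dose level is not fixed for a subject. SAP 3.1.1 says "Intra-subject dose escalation to the next PEGPH20 dose studied may be allowed", subject to the Investigator's judgement, discussion with the Sponsor, and the next dose not having exceeded the MTD. Protocol 6.1.1 says the same. SAP 4.4.2, which defines the population used for drug exposure, says "Subjects will be analyzed according to the initial cohort actually assigned".

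SAP 4.9.2 also tabulates omitted doses (with reasons), dose reductions, delays and interruptions. It has no row for escalations and does not say against which level a reduction is judged.

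**The concern.** RDI should compare the dose delivered with the dose planned for the same subject over the same period. After an escalation the two sides of the SAP's ratio refer to different plans: the numerator contains the higher doses and the denominator stays at the starting level. A fully dosed subject then exceeds 100%, and one who misses doses at the higher level can look fully dosed against the lower one. Because the top class is open-ended, the class counts do not show that this has happened. With no count of escalations, a reader who sees a value above 100% in the descriptive summary cannot tell why.

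What is at stake is the reported deliverability of PEGPH20 in the Dose Escalation portion. The effect does not depend on which body weight is used; it arises even when weight never changes.

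**Working it through.** The documents give no numerical RDI, so there is no figure to reproduce. The check applies the SAP 4.9.2 formulas to stated scenarios.

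**Inputs from the documents.** Dose levels 1.6, 2.2, 2.6, 3.0 and 4.0 µg/kg; three PEGPH20 doses per 21-day cycle (SAP 3.1.1). Adjusted cycles = (end of last cycle − first dose date + 1)/21.

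**Assumptions.** Visits on schedule, stable weight, six cycles, one step up from Cycle 3. On schedule, adjusted cycles = 126/21 = 6.

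**Formula check without escalation.** At 1.6 µg/kg with all 18 doses given: cumulative 28.8, ADI 28.8/6 = 4.8, PDI 1.6 × 3 = 4.8, RDI 100%. With one of three doses omitted in every cycle: cumulative 19.2, ADI 3.2, RDI 66.7%. The formula behaves properly when the level does not change.

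**Escalation 1.6 to 2.2, all doses given.** Cumulative = 6 × 1.6 + 12 × 2.2 = 36.0; ADI = 36.0/6 = 6.0. SAP PDI = 4.8, so RDI = 125.0%. PDI from the assigned levels = 36.0/6 = 6.0, so RDI = 100%.

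**Same subject, one omission in each escalated cycle (4 of 18).** Cumulative = 36.0 − 4 × 2.2 = 27.2; ADI = 4.533. SAP RDI = 4.533/4.8 = 94.4%. RDI from the assigned levels = 4.533/6.0 = 75.6%.

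**All four single steps**

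| Step (µg/kg) | Full cumulative | SAP PDI | PDI from assigned levels | SAP RDI, full dosing | SAP RDI, 4 of 18 omitted | RDI from assigned levels, 4 of 18 omitted |
|---|---|---|---|---|---|---|
| 1.6 to 2.2 | 36.0 | 4.8 | 6.0 | 125.0% | 94.4% | 75.6% |
| 2.2 to 2.6 | 44.4 | 6.6 | 7.4 | 112.1% | 85.9% | 76.6% |
| 2.6 to 3.0 | 51.6 | 7.8 | 8.6 | 110.3% | 84.6% | 76.7% |
| 3.0 to 4.0 | 66.0 | 9.0 | 11.0 | 122.2% | 92.6% | 75.8% |

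With full dosing, RDI from the assigned levels is 100% in every row. With four omissions every subject belongs in the 70% to <80% class. The SAP formula puts two of the steps in ≥90% and the other two in 80% to <90%.

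**Sensitivity.** With full dosing and escalation from Cycle 3, totals of four to eight cycles give SAP values from 107.7% (2.6 to 3.0, four cycles: mean level 2.8, and 2.8/2.6) to 128.1% (1.6 to 2.2, eight cycles: mean level 2.05, and 2.05/1.6). With 2 of 18 doses omitted, 1.6 to 2.2 over six cycles gives (36.0 − 4.4)/6 = 5.267, which is 109.7% under the SAP and 87.8% from the assigned levels.

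**How much omission the ratio can absorb.** For cycles given wholly at the higher level b against a starting level a, RDI stays at 100% until a share 1 − a/b of doses is omitted: 27.3%, 15.4%, 13.3% and 25.0% for the four steps. It stays at or above 90% until a share 1 − 0.9a/b is omitted: 34.5%, 23.8%, 22.0% and 32.5%.

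**The case against.** **The sentence does not say initial level.** This is true. The reading rests on the words "the planned dose intensity per cycle (ug/kg) for each individual dosing cohort will be calculated as" taken together with SAP 4.4.2. The other reading does not rescue the formula: if the current level were meant, one value per cohort still could not describe a subject who has had two levels.

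**RDI against the starting dose is a coherent descriptive choice, and a value above 100% is visible.** This is partly fair. The descriptive RDI summary would show such values. The class table would not, and an escalated subject with omissions may fall below 100% and give no sign of a problem.

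Three stronger readings are tempting, and the documents do not support them.

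- *Omitted doses disappear from the report.* They do not. SAP 4.9.2 tabulates subjects with an omission, the number and percentage of doses omitted, and the reasons, with separate rows for reductions, delays and interruptions. Omissions are offset only within RDI and its classes.
- *The error bears on the RP2D.* Protocol 6.1.1 does say "Safety data from all subjects dosed will be reviewed to determine the RP2D", but the same section bases the expansion dose on Cycle 1 safety data, at a meeting within 10 business days of the end of the last cohort. Escalation requires the next level to have been cleared first. The SAP is dated 19 April 2019, after enrolment had stopped on 31 May 2018 with Dose Expansion already under way. An RDI computed under this SAP could not have informed that choice.
- *Toxicity at the higher dose is charged to the lower one.* No SAP table does this. Adverse events and exposure are shown by cancer type and in total (SAP 4.9, 4.9.2 and 4.9.4). The only safety table by dose level is for DLTs, which covers 21 days from the first PEGPH20 dose. Protocol 11.1.7 and 11.1.8 do call for summaries by dose level, but they do not say that the initial level is meant.

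Nor does every escalated subject exceed 100%: with enough omissions the value is inflated but below 100%, as the table shows.

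**Conclusion.** The point stands as an error in one descriptive statistic. Followed as written, SAP 4.9.2 gives an RDI that is too high for every Dose Escalation subject who escalates. One step up from Cycle 3 of 6 with full dosing gives about 110% to 125% instead of 100%. With omissions, a subject can land one or two classes too high.

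The size rests on the assumed scenarios (on-schedule visits, stable weight, time of escalation) and on reading the dose level as that of the initial cohort. The documents do not say how many subjects escalated, if any, so the effect on the summary as a whole cannot be given. Hypothesis tests, sample size, the DLT rule, efficacy results and the Dose Expansion RDI are unaffected. The correction is worth making because the formula is wrong for a situation that the plan itself allows, and the remedy is cheap.

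**What to change.** In SAP 4.9.2, define Dose Escalation PEGPH20 planned dose intensity as the sum, over planned visits, of the dose level assigned at that visit, divided by the same adjusted cycles. Change the assigned level only for intra-subject escalation allowed by the protocol, not for toxicity reductions.

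The wording of planned visits needs care. They should be the visits that a 21-day calendar places in the adjusted treatment period. If only visits in cycles actually started are counted, the adjusted cycles cancel and a delay no longer lowers RDI. For example, take six fully dosed cycles at 1.6 µg/kg with an assumed 14-day delay. Adjusted cycles are (126 + 14)/21 = 6.67 and ADI is 28.8/6.67 = 4.32, so the SAP gives 4.32/4.8 = 90%; after cancelling it would read 100%. Writing PDI as 3 × the mean assigned level over the planned visits avoids this. It equals the sum form for complete on-schedule cycles and leaves subjects who never escalate exactly as they are now.

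Also:

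- tabulate or flag subjects who escalate;
- count a return from the escalated level as a dose reduction, and state the reference level for reductions;
- keep the initial cohort for DLTs.

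The cost is SAP wording and modest programming. Protocol 8.5 says that administration data are recorded in the eCRF. Neither document says that an assigned level per cycle is recorded, so the escalation date may have to be derived from dosing records or from the Sponsor discussion that escalation requires. None of this implies a view on any dose.
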